1.0 BACKGROUND

In the last 5-10 years, there has been a significant shift in the radiation of women with intact breast cancer to shorter, more cost effective and convenient treatment courses. Through the work of several prospective published trials, this concept has been found to be safe and effective in women undergoing breast conserving therapy.[1-4] Decreasing the time required for women to undergo post mastectomy radiation decreases health care costs, and allows patients to spend more time out side of the healthcare setting, ultimately improving patient, employer and payer satisfaction. As the outcomes with traditional post mastectomy are already considered safe and effective, this trial is designed as a non-inferiority trial to ensure that a shorter time course of radiation is as safe as the current standard of care. Although there are limited data from Europe that support this concept in mastectomy and regional nodal irradiation (RNI) patients, no studies have been done in the setting of breast reconstruction. We need prospective randomized data using modern radiotherapy and chemotherapy before widespread adoption occurs here in the United States and elsewhere. Post Mastectomy Radiation Therapy (PMRT) in this setting is a combination of all hypofractionation challenges, combining concerns over adjuvant chemotherapy, post mastectomy chest wall, supraclavicular fossa, internal mammary nodes and reconstructed breast short course radiation. Each of these factors independently is a potential contraindication to hypofractionated radiation due to a lack of data. There are two pressing and currently outstanding questions related to hypofractionation that require resolution in a phase III setting:

- 1) What is the rate of radiation related complications in reconstructed chest walls treated with shortened course radiotherapy?
- 2) Is hypofractionation safe when treating regional nodal volumes (where the brachial plexus is located)?

These two questions have been contentious, and their uncertainty will directly affect patient care for years to come, unless a well-designed study can define the unknowns. In this study, both of these questions will be tested and resolved as primary and secondary endpoints. This trial design also collects much needed prospective data regarding the true complication rates for PMRT with breast reconstruction, given the multitude of options for breast reconstruction timing and techniques.

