2.2 Secondary Objectives

- 2.2.1** To evaluate the incidence of acute and late radiation complications based on CTCAE 4.0 toxicity.
- 2.2.2** To evaluate the local and local regional recurrence rate.
- 2.2.3** To compare reconstruction complication rates based on reconstruction method (autologous +/- implant vs implant only) and timing of reconstruction received (immediate vs. intent for delayed).

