5.0 STUDY CALENDAR

The pre-study testing intervals are guidelines only. Laboratory and clinical parameters during treatment are to be followed using individual institutional guidelines and the best clinical judgment of the responsible physician. It is expected that patients on this study will be cared for by physicians experienced in the treatment and supportive care of patients on this trial.

Pre-Study Testing Intervals

- To be completed ≤ 7 DAYS before registration: Pregnancy test,
- To be completed ≤ 28 DAYS before registration: history and physical.

	Prior to Registration	Before RT [¥]	At completion of RT [€]	2 to 8 weeks post RT	6, 12, 18 mos. post RT*	2 years post RT*	30 mos., 3,4 and 5 years post RT**	10 and 15 years post RT***
Tests & Observations								
H&P, Weight, PS	X	X (1)	X	X	X	X	X	
Height	X							
Mastectomy or reconstruction complications		X	X	X	X	X	X	
Recurrence (scan or clinical) Assessment					X	X	X	X
Adverse Events Assessment		A	A	A	A	A	A	
Clinical Lymphedema Assessment		B	B	B	B	B	B	
Cardiac and Brachial Plexopathy Events					C	C	C	C
Arm Circum. Measure (see §10.5)		X			X (2)	X		
Photographs for Cosmetic Assessment		D				X (4)		
Laboratory Studies								
Serum or Urine HCG	E							
Hemoglobin A1C	F							
Questionnaires								
Breast-Q Post-mastectomy		G						
Breast-Q Post-reconstruction		G				X	X (3)	
LBCQ		X			X (2)	X	X (3)	
BLE		H			X (2)	X	X (3)	
Economic Surveys		I	J	I	J			
EQ-5D-3L		X			X	X		
Was It Worth It Questionnaire						X		
Correlative Study (optional)	To be collected at baseline, see Sections 6.2 and 13.1							
Whole Blood								

¥ May be completed at any time following patient consent (before or after registration, but prior to treatment)

€ May be completed within 72 hours of last radiation treatment.

* +/- 6 weeks.

** For 30-month visit, +/- 6 weeks; for 3, 4, and 5-year visits, +/- 3 months

*** +/- 6 months. All follow up, including survival status, done after 5 years will be gathered by record review only.

A Assessment of side effects related to radiation therapy should be assessed according to the history and physical examination.

B To be assessed per the CTCAE criteria.

C Will be assessed by medical record review.

D Only for patients with final reconstruction completed before radiation.

E For women of childbearing potential. Must be done within 7 days prior to registration.

F For diabetic patients only, to be done ≤ 90 days before registration.

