9.1 Routine Adverse Event Reporting

Adverse event data collection and reporting, which are required as part of every clinical trial are done to ensure the safety of patients enrolled in the studies as well as those who will enroll in future studies using similar agents. Adverse events are reported in a routine manner at scheduled times according to the study calendar in Section 5.0. For this trial, Solicited Adverse Event Solicited form is used for routine AE reporting in Rave.

Acute Adverse Events: Acute adverse events, will be scored per CTCAE 4.0 regardless of attribution. Attribution will however be collected for separate analysis.

Late Radiation Adverse Events: Late radiation complications will be defined as those that are present ≥ 6 months after the final dose of radiation and include CTCAE 4.0 grade 3+:

9.2 Solicited Adverse Events:

The following adverse events are considered "expected" and their presence/absence should be solicited, and severity graded, at baseline and for each cycle of treatment.

9.2.1 Radiation Therapy Complications:

CTCAE v4.0 Term	CTCAE v4.0 System Organ Class (SOC)
Fibrosis, deep connective tissue	Musculoskeletal and connective tissue disorders
Superficial soft tissue fibrosis	Musculoskeletal and connective tissue disorders
Chest wall pain	Musculoskeletal and connective tissue disorders
Joint range of motion decreased	Musculoskeletal and connective tissue disorders
Wound Infection	Infections and infestations
Fatigue	General disorders and administration site conditions
Dermatitis radiation	Injury, poisoning and procedural complications
Wound complication	Injury, poisoning and procedural complications
Wound dehiscence	Injury, poisoning and procedural complications
Lymphedema	Vascular disorders
Telangiectasia	Skin and subcutaneous tissue disorders
Hypothyroidism	Endocrine Disorders
Myocardial Infarction	Cardiac disorders
Cardiac disorders – Other specify*	Cardiac disorders
Pulmonary fibrosis	Respiratory, thoracic and mediastinal disorders
Brachial Plexopathy	Nervous system disorders
Peripheral motor neuropathy	Nervous system disorders
Peripheral sensory neuropathy	Nervous system disorders
Treatment related secondary malignancy	Neoplasms benign, malignant and unspecified (including cysts and polyps)

* Specific cardiac events, if and when they occur will be recorded on the Adverse Events: Other form.

9.2.2 Non CTCAE RT Associated Complications:

- a) Shoulder stiffness (occasional) (Grade 1-3)

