10.2 Acute and Late Radiation Complications

Acute Adverse Events: Acute adverse events, will be scored per CTCAE 4.0 regardless of attribution. Attribution will however be collected for separate analysis.

Late Radiation Adverse Events: Late radiation complications will be defined as those that are present ≥ 6 months after the final dose of radiation and include CTCAE 4.0 grade 3+:

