12.4 Supplementary/Secondary Analysis Plans

12.4.1 Secondary Objectives

Incidence of acute and late radiation complications based on CTCAE 4.0 toxicity. The proportion of patients with acute or late radiation complications, will be estimated separately by treatment arm and will be compared across the two arms using two-sample test of proportions (Z test) with a two-sided alternative.

Local and local regional recurrence rate: The cumulative incidence of local and local regional recurrence will be estimated separately by treatment arm using the cumulative incidence function treating death as the competing risk and will be compared using Gray's test. In addition, local and local regional recurrence free survival will be summarized for each arm using the Kaplan-Meier estimators, and will be compared using a log rank test.

Reconstruction complication rates based on reconstruction method (autologous +/- implant vs. implant only) and timing of reconstruction received (immediate vs. intent for delayed): Between-arm differences in reconstruction complication rates will be assessed separately within each of the six subgroups based on type and timing of reconstruction. Between-arm differences in complication rates will also be assessed within the two broader subgroups of patients who receive implant only and those who receive autologous based reconstruction. Within each subgroup, the comparison will be done using a two-sample Z test of proportions with a two-sided alternative as described for the primary analysis in Section 12.3.2.

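### The Background says nodal (brachial plexus) safety will be resolved, but section 12 specifies no plexopathy analysis or upper bound, and the only test that reaches plexopathy pools it with all radiation complications

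*Combined protocol and SAP*

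**What the plan says.** Section 1.0 of the protocol poses two questions for the trial. The second is "Is hypofractionation safe when treating regional nodal volumes (where the brachial plexus is located". It adds: "In this study, both of these questions will be tested and resolved as primary and secondary endpoints".

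The matching secondary objective in 2.2 does not name plexopathy: "To evaluate the incidence of acute and late radiation complications based on CTCAE 4.0 toxicity". The analysis in 12.4.1 reads "The proportion of patients with acute or late radiation complications, will be estimated separately by treatment arm", and the proportions "will be compared across the two arms using two-sample test of proportions (Z test) with a two-sided alternative". It gives no event list, time point, margin, confidence bound or alpha. Section 10.2 states no grade floor for acute events; late complications are "defined as those that are present ≥ 6 months after the final dose of radiation and include CTCAE 4.0 grade 3" or higher.

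The data are collected. "Brachial Plexopathy" is a solicited term in the table in 9.2.1. The study calendar (5.0) has a row for "Cardiac and Brachial Plexopathy Events", assessed by record review from 6 months to 15 years.

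**The concern.** The first of the two questions, on reconstruction complications, gets a margin, an alpha, a power and a decision rule in 12.2 and 12.3.2. The second gets no analysis of its own. Plexopathy appears to be rare on the protocol's own evidence: none in the 40 Gy trial (1.1), and none among 290 nodally treated patients in the first report of the companion trial, with one case by 10 years (1.3). A handful of such events added to a much commoner category barely moves the pooled proportion, and late plexopathy below grade 3 does not enter the late category at all. Followed as written, the plan would collect plexopathy for 15 years and still have no prespecified statement about its rate in the hypofractionated arm.

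**Working it through.** **Inputs.** Evaluable 396 per arm and accrued 440 per arm (12.2). Expected combined late toxicity 7-10% (1.2), used here as the base rate of the pooled endpoint. That is an assumption: the 7-10% refers to grade 2 or higher non-acute toxicity, whereas the endpoint combines acute events of unstated grade with late events from grade 3. Two-sided alpha 0.05 is assumed. An excess plexopathy case is assumed to occur in a patient with no other counted complication.

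**The plan's own figure.** The only powered comparison is the primary one. With control rate 0.25, margin 0.10, one-sided alpha 0.025 and 90% power, n = (1.960 + 1.282)² × 2 × 0.25 × 0.75 / 0.10² = 394.03, or 395 per arm against the stated 396. Power at 396 is 90.1%. At a 50% control rate it is 80.4% (stated as about 80%). The plan's figures reproduce. No power or precision is stated for radiation complications or plexopathy.

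**Pooled test, 1-point excess.** Power is approximately Φ[(d − 1.96 × SE0)/SE1], where d is the true difference, SE0 the pooled standard error and SE1 the unpooled one. For 7% v 8% at 440 per arm, SE0 = √(2 × 0.075 × 0.925/440) = 0.01776 and SE1 = 0.01775. Then (0.01 − 0.03481)/0.01775 = −1.40, which gives 8.1%. Exact enumeration of the two binomials, counting both tails, gives:

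| Base v base + 1 point | 396 per arm | 440 per arm |
|---|---|---|
| 7% v 8% | 8.3% | 8.8% |
| 10% v 11% | 7.4% | 7.8% |
| 25% v 26% (assumed, if acute events are common) | 6.2% | 6.4% |
| 50% v 51% (same) | 6.0% | 5.7% |

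These are little above the 5% error rate. Detecting the 1-point excess with 80% power would need about 10,900 per arm on a 7% base and 14,800 on a 10% base. At 396 per arm, the smallest pooled increase detectable with 80% power is 6.0 points (7% base) to 6.8 points (10% base).

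**Plexopathy tested alone.** The documents give no usable rate, so all rates are assumed. Power by exact enumeration of the Z test:

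| Arm 1 v Arm 2 | 396 per arm | 440 per arm |
|---|---|---|
| 0.5% v 1% | 11% | 12% |
| 0.5% v 1.5% | 27% | 30% |
| 0.5% v 2% | 47% | 51% |
| 0% v 1% | 56% | 64% |
| 0.1% v 2% | 85% | 88% |

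Fisher's exact test is lower: at 440 per arm, 5% for 0.5% v 1% and 41% for 0.5% v 2%.

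**Estimation instead.** With zero events in n fully followed patients, the Clopper-Pearson two-sided 95% upper limit is 1 − 0.025^(1/n). This gives 0.93% for n = 396, 0.83% for n = 440, and 1.19% for n = 308 (440 × 0.70, assuming 30% are no longer followed). One event gives 1.40% at 396 and 1.26% at 440; two give 1.81% and 1.63%. With no events in either arm of 396, the Newcombe 95% upper limit for the difference is 0.96 points.

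**The case against.** A reader might infer that a non-significant pooled comparison would be reported as showing nodal safety. The documents do not support that. No section states such a rule; 1.6 only hypothesises a similar toxicity rate, and 12.4.1 calls for estimates by arm before any test.

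A reader might also say there is almost no power against plexopathy however it is analysed. That holds for the pooled test but not in general: for plexopathy alone, power runs from about 11% to 88% over the assumed rates above.

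It can fairly be added that 12.4.1 does not forbid tables by event term, that plexopathy is recorded as its own term so counts by arm could be produced, and that the monitoring board receives adverse event reports every six months (12.7.1). Nodal safety is also wider than the plexus: lymphedema has its own planned analyses in 12.4.3. Finally, this is an unpowered secondary safety outcome, and the primary conclusion does not depend on it.

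All of this stands, and it narrows the point. It does not remove it: a table the plan does not call for is not a prespecified answer, and it supplies no bound for a question that 1.0 says the trial will resolve.

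**Conclusion.** The concern holds as a gap between a stated promise and the analysis plan. The pooled test has about 7-9% power for a 1-point plexopathy excess at 396 to 440 per arm, and about 6% if acute events push the base to 25-50%. It also leaves out late plexopathy below grade 3. It therefore cannot resolve the plexus question, whichever way it falls. The size rests on the assumed alpha, the borrowed 7-10% base and non-overlapping excess cases. A 5% base would raise the figure only to 9-10%. The gap concerns plexopathy only; it does not reach lymphedema or the primary endpoint. It should be corrected, because the data are already on the calendar and an upper limit of about 1% is attainable at the planned size if no cases are seen and follow-up is complete.

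**What to change.** In 12.4.1, add brachial plexopathy of any grade as a separate safety estimate:

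- Report by arm the number of cases, the number of patients still under follow-up, and the cumulative incidence at stated calendar times, for example 2, 5 and 10 years.
- Use an estimator that handles censoring and treats death as a competing event, with two-sided 95% limits throughout. Use Clopper-Pearson limits only where follow-up to the time point is complete. This matters because 11.3 ends follow-up at recurrence, contralateral or second primary cancer, or alternative treatment, and after 5 years it is by record review only.
- Give a 95% confidence interval for the between-arm difference.
- State that plexus safety will be described by these upper limits and not by a non-significant pooled test.

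The cost is some analysis-plan wording and one small table; no new patients or visits are needed, and the primary analysis and its alpha are untouched. The downside is a more limited claim, that a rate above a stated figure is excluded, with limits that widen at the later times.

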12.2 Sample Size, Accrual Time and Study Duration

Our target sample size will be 792 evaluable patients (396 in each arm). To account for 10% drop-out due to cancellations or protocol deviations, our target accrual is 880 patients (440 per arm) (90% of 880 is 792).

The study design is a randomized, un-blinded, non-inferiority trial. It is assumed that the two-year breast reconstruction complication rate for the control arm (Arm 1: standard fractions) is 25%. Other assumptions for the sample size determination include:

- α (one-sided) = 0.025
- power = 90%
- non-inferiority margin: the absolute increase in the proportion of patients who experience
- a breast reconstruction complication within two-years is 10% above that of the control arm.
- one interim analysis (when 30% of the information is obtained) for futility

Under an alternative hypothesis that the true rates in the two arms are equal, a sample size of 792 (396 per arm) evaluable patients would give us 90% power to reject the null hypothesis of inferiority. The final analysis will take place after all patients have reached two years post-radiation. The anticipated accrual period is approximately 30 months, and the total study duration is approximately 60 months. We anticipate being able to accrue approximately 30 patients per month based on our best estimate extrapolated from recently closed intact breast trials looking at similar fractionations. It should be noted that if we instead assumed a complication rate of 50% in the control arm (the most statistically conservative, in terms of sample size), the above sample size would still give us approximately 80% power to reject the null hypothesis of inferiority (again with one-sided α of 0.025).

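### Late radiation complications are planned as an undated crude proportion, so the per-arm figure is not an incidence at any defined time and depends on accrual and lock date

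*Combined protocol and SAP*

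**What the plan says.** The objective in section 2.2.1 is "To evaluate the incidence of acute and late radiation complications based on CTCAE 4.0 toxicity". It names no time point.

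Section 10.2 sets the start but not the end of the late period: "Late radiation complications will be defined as those that are present ≥ 6 months after the final dose of radiation". It restricts these events to grade 3 or higher. The study calendar (section 5.0) has adverse events assessed at visits up to 5 years.

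The analysis in section 12.4.1 is a proportion per arm ("The proportion of patients with acute or late radiation complications, will be estimated separately by treatment arm"), compared by a "two-sample test of proportions (Z test) with a two-sided alternative". No window, denominator or rule for unequal follow-up is given, and acute and late events are covered by the same sentence.

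Two statements in section 12.2 set the timing of the final analysis: "The anticipated accrual period is approximately 30 months, and the total study duration is approximately 60 months", and "The final analysis will take place after all patients have reached two years post-radiation". Section 12.4.1 gives no separate date for the toxicity analysis.

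Sections 11.3.1 and 11.3.2 end follow-up at disease recurrence, contralateral breast cancer, a non-breast second primary or alternative treatment. Under section 11.4.2, patients who never start radiation need only baseline, off-treatment and end-of-study forms.

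The next paragraph of section 12.4.1 treats recurrence differently: "The cumulative incidence of local and local regional recurrence will be estimated separately by treatment arm using the cumulative incidence function", with death as a competing risk and Gray's test.

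**The concern.** An incidence needs a time horizon. Here events can accumulate without an upper limit while patients are watched for different lengths of time, and the estimator divides events by patients regardless. Two trials with identical toxicity but different accrual speed or lock dates would report different rates.

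The omission stands out within the plan. The primary endpoint is tied to two years (12.3.2), cosmesis to 24 months (12.4.2) and arm lymphedema to 2 years (12.4.3), and recurrence has a time-to-event method. Late toxicity has neither.

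What is at stake is the main description of late safety for the shorter schedule. Section 1.0 names safety of nodal treatment near the brachial plexus as one of two questions the trial should settle. Section 1.3 notes that one cited UK hypofractionation trial had no plexopathy in its initial report and one case at 10 years. Section 1.2 lists 5-year toxicity figures, and an undated proportion cannot be set beside them.

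**Working it through.** **The plan's own figures.** No sample size, power or dated rate is given for late complications, so there is nothing to reproduce for this endpoint. The primary-endpoint figures do reproduce. n per arm = (1.960 + 1.282)² × 2 × 0.25 × 0.75 / 0.10² ≈ 394 to 395, against 396 stated, and 792 / 0.90 = 880.

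**Follow-up at the final analysis (derived, not stated).** The last patient has 24 months. The first has 24 + 30 = 54 months. At the stated accrual ("We anticipate being able to accrue approximately 30 patients per month"), 880 / 30 = 29.3 months, so the longest is 53.3. If the analysis instead falls at study month 60, the range is about 27 to 57, assuming about 3 months from registration to the end of radiation. Patients whose follow-up is stopped by the protocol have less.

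**What the crude proportion estimates.** Let F(t) be the cumulative incidence t months after radiation. With even accrual and no early exit, the expected proportion is the mean of F(u) over u from 24 to 54.

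Under a constant hazard λ from month 6, scaled to an assumed 5-year incidence of 10%:
- λ = −ln(0.90) / 54 = 0.00195 per month
- F(24) = 1 − exp(−18λ) = 3.5%
- F(54) = 1 − exp(−48λ) = 8.9%
- mean = 1 − [exp(−18λ) − exp(−48λ)] / (30λ) = 1 − (0.9655 − 0.9106) / 0.0585 = 6.2%

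That is 62% of the 5-year value, a relative shortfall of 38%. An assumed 7% gives 4.3%, also 62%. The 7-10% in section 1.2 concerns grade 2 or higher, so it serves for scale only.

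**Dependence on the hazard.** The documents give no hazard, so its shape was varied (5-year incidence 10%, follow-up 24 to 54 months):

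| Assumed hazard from month 6 | F(24) | Crude proportion | Shortfall against 5 years |
|---|---|---|---|
| 20 times higher in months 6-24 | 9.1% | 9.5% | 5% |
| 10 times higher in months 6-24 | 8.4% | 9.1% | 9% |
| 5 times higher in months 6-24 | 7.2% | 8.4% | 16% |
| Weibull, shape 0.25 | 7.7% | 8.8% | 12% |
| Weibull, shape 0.5 | 5.9% | 7.8% | 22% |
| Constant | 3.5% | 6.2% | 38% |
| Weibull, shape 1.5 | 2.0% | 5.0% | 50% |
| Weibull, shape 2 | 1.2% | 4.1% | 59% |

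In the constant and Weibull cases the crude figure equals F at roughly month 38 to 40, a horizon nobody chose. With follow-up of 27 to 57 months and a constant hazard it is 68% of the 5-year value instead of 62%, so the lock date alone moves it.

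**Events already present at month 6.** Section 10.2 counts presence, not onset, so an earlier event that persists qualifies at once. If a share m of the 5-year total is present at month 6 and the rest follows the constant-hazard pattern, the shortfall is about (1 − m) × 38%: 28%, 19% and 9% for m = 25%, 50% and 75% (assumed values).

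**Early end of follow-up.** If 5%, 10% or 20% of patients leave by month 24 at a constant rate (assumed) and stay in the denominator, the constant-hazard figure of 6.2% falls to 5.9%, 5.6% or 5.0%.

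**The comparison.** With the same event rate in both arms (6.2%, 396 per arm), the simulated two-sided type I error of the Z test is 5.0%.

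**The case against.** The strongest reply is that this is only a missing time point for a secondary endpoint. Nothing in the plan says the proportion estimates a 5-year rate, so falling short of one is not an error against a stated target. Randomisation balances administrative follow-up, so the test is sound. Section 12.4.1 does not say when late toxicity is analysed; if every patient had 5 years of follow-up and nobody left early, the proportion would equal the 5-year incidence. Naming a 24-month window would remove the unequal administrative follow-up and keep the Z test.

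Most of this stands as a limit on the claim. The 24-54 month range assumes analysis at the final lock, the 5-year value is a yardstick chosen for comparison, and the type I error is not affected under equal follow-up. It does not remove the defect: the objective is an incidence, and the planned estimate has no horizon. A fixed 24-month window would also leave patients whose follow-up the protocol ends earlier counted as event-free or dropped, with no rule to say which.

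A reader might also treat the 10% allowance in section 12.2 as loss before month 6 and derive a larger shortfall. The documents do not support that. The allowance is for cancellations and protocol deviations, carries no timing, and some deviating patients stay in follow-up (section 7.4, scar boost). Nor does section 12.4.1 say that early leavers remain in the toxicity denominator; the all-randomised rule in section 12.3.2 is written for the primary analyses.

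**Conclusion.** The concern holds as a defect of the per-arm estimates. The planned proportion mixes cumulative incidence over about 24 to 54 months, shifts with accrual and lock date, and is not an incidence at any defined time. Every hazard pattern in the table puts it below the 5-year incidence. The size rests on an unstated hazard: about 5% to 59% relative, and 38% under a constant hazard from month 6. These are scenario values, not bounds; the shortfall would shrink further if most qualifying events were already present at month 6.

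Two stronger readings are tempting. One is that late toxicity will be understated by well over a third. That holds only for a constant or rising hazard with few events present at month 6, and the documents supply no hazard. The other is that the comparison between arms is invalid. It is not: the Z test keeps its level unless early end of follow-up differs by arm, and the documents give no evidence that it would.

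**What to change.** In section 12.4.1, separate late from acute complications and make these changes for the late ones:

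- Estimate the cumulative incidence function from the end of radiation, among patients who started radiation, using time to first qualifying event. Count events present at the 6-month visit from month 6.
- Treat death as a competing event. State how recurrence, second cancer and alternative treatment are handled, either as competing events or as censoring with a sensitivity analysis. Treating only death as competing would leave possibly informative censoring unaddressed.
- At the final analysis, report the 24-month value by arm with confidence intervals and compare arms by Gray's test. Report the 60-month value only once 5-year follow-up is available, since no patient has more than about 54 months at that lock.
- Keep the two-sided Z test for acute complications.

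The cost is a short change of SAP wording and a method already planned for recurrence. Adverse events are already assessed at scheduled visits, so no new data collection should be needed, provided the visit or onset date of each late event is recorded.
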